## 3. Analysis Population

The Intent-to-treat principle will be followed to define the analysis population. All subjects who signed the informed consent and in whom Trevo® Retriever was deployed through the microcatheter are considered enrolled and will be included in all the analyses.

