## 4. Sample Size and Power

There will be no sample size/or power estimation for this single-arm registry. Two hundred subjects will be enrolled at up to 15 centers in China.

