#### 5.2.2. Secondary Endpoints Definition

1. Day 90 mRS (good clinical outcomes defined as mRS of 0-2).
2. Day 90 mortality.

If the subjects had completed their 90-day visit, the subjects will be considered as alive at Day 90. If the subjects did not come for their Day 90 visit and died, the date of death will be used to compare with the upper window of their Day 90 (90 + 14 days post procedure). If the subjects died after the upper window of their Day 90, the subjects will be considered as alive at their Day 90. Otherwise, the subjects will be counted as death before Day 90.

3. Neurological deterioration at 24 hours which is defined as four or more points increase in the NIHSS score from the baseline to 24 hours post procedure.

STRYKER CONFIDENTIAL - THIS DOCUMENT CONTAINS CONFIDENTIAL AND PROPRIETARY INFORMATION THAT IS THE PROPERTY OF STRYKER CORPORATION. NEITHER THIS DOCUMENT NOR THE INFORMATION HEREIN MAY BE REPRODUCED, USED, OR DISCLOSED TO ANY THIRD PARTY WITHOUT THE PRIOR WRITTEN CONSENT OF STRYKER CORPORATION

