**Table 1 Subjects Disposition**

	Number of Subjects Enrolled (N=xxx*)	Subjects Eligible at 24 Hours (-6/+24) post procedure (N=xxx*)	Subjects Eligible at Discharge/Day 5-7 (whichever comes first) (N=xxx*)	Subjects Eligible at Day 30 (N=xxx*)	Subjects Eligible at Day 90 (N=xxx*)
Visit Completed	xx (xx.x%)	xx (xx.x%)	xx (xx.x%)	xx (xx.x%)	xx (xx.x%)
Visit Not Completed	xx (xx.x%)	xx (xx.x%)	xx (xx.x%)	xx (xx.x%)	xx (xx.x%)
Reason for not completing the visit					
Missed Visit	NA	xx (xx.x%)	xx (xx.x%)	xx (xx.x%)	xx (xx.x%)
Early Termination	NA	xx (xx.x%)	xx (xx.x%)	xx (xx.x%)	xx (xx.x%)
List Reason for Early Termination **	NA	xx (xx.x%)	xx (xx.x%)	xx (xx.x%)	xx (xx.x%)
*: N = Number of subjects expected at this visit					
**: The percentage is calculated based on the number of early terminations.					

STRYKER CONFIDENTIAL - THIS DOCUMENT CONTAINS CONFIDENTIAL AND PROPRIETARY INFORMATION THAT IS THE PROPERTY OF STRYKER CORPORATION. NEITHER THIS DOCUMENT NOR THE INFORMATION HEREIN MAY BE REPRODUCED, USED, OR DISCLOSED TO ANY THIRD PARTY WITHOUT THE PRIOR WRITTEN CONSENT OF STRYKER CORPORATION

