**Ver AA**

**Table 11: Secondary endpoints**

Secondary Endpoints	% of Subjects with Clinical Outcomes (n/N)*
mRS** of 0-2 at Day 90	xx.x% (xx/xxx)
Mortality rate at Day 90	xx.x% (xx/xxx)
Neurological deterioration at 24(-6/+24) hours	xx.x% (xx/xxx)
Study Device and procedure related SAE	xx.x% (xx/xxx)

\*:95% CI will be generated as needed for ad hoc analysis  
\*\*: LOCF is used for Day 90 mRS.

STRYKER CONFIDENTIAL - THIS DOCUMENT CONTAINS CONFIDENTIAL AND PROPRIETARY INFORMATION THAT IS THE PROPERTY OF STRYKER CORPORATION. NEITHER THIS DOCUMENT NOR THE INFORMATION HEREIN MAY BE REPRODUCED, USED, OR DISCLOSED TO ANY THIRD PARTY WITHOUT THE PRIOR WRITTEN CONSENT OF STRYKER CORPORATION

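### The Day 90 mortality rule gives no sound status to a subject who misses Day 90 and has no recorded death, and known deaths are not tied to the carried-forward mRS

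*SAP*

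**What the plan says.** SAP 5.2.2, item 2, sets Day 90 vital status in four sentences:

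1. "If the subjects had completed their 90-day visit, the subjects will be considered as alive at Day 90".
2. "If the subjects did not come for their Day 90 visit and died, the date of death will be used to compare" with the upper end of the Day 90 window, which is Day 104.
3. "If the subjects died after the upper window of their Day 90, the subjects will be considered as alive at their Day 90".
4. "Otherwise, the subjects will be counted as death before Day 90".

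On the analysis set, SAP 3 says that consented subjects in whom the device was deployed "are considered enrolled and will be included in all the analyses". SAP Table 11 shows mortality as n/N without defining N. The table's only missing-data rule is a footnote: "LOCF is used for Day 90 mRS".

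The plan expects incomplete follow-up. SAP Table 1 has a block headed "Reason for not completing the visit", with rows for missed visits and early termination. Protocol 7.2 stops follow-up of withdrawn subjects and does not replace them. SAP 6.2 allows the final report to include subjects who terminated before Day 90.

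**The concern.** A subject who misses Day 90 and has no recorded death meets neither condition for being alive. Whether the last sentence of the rule reaches that subject depends on how the word *Otherwise* is read, and no other section settles it. The same data could therefore give more than one mortality rate.

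Day 90 all-cause mortality is a named secondary endpoint of a single-arm registry. With no control arm, the absolute rate is the result. SAP 2.1.2 foresees use of the data in regulatory submissions and reimbursement dossiers.

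A second gap sits beside it. Appendix F of the protocol scores death as mRS 6, and SAP Table 7 has a Day 90 row for 6. The SAP does not say, however, that a known death is coded 6 before LOCF is applied. A subject with a Day 30 mRS of 0-2 who later dies could then count as a good outcome in the first row of Table 11 and as a death in the second.

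**Working it through.** The documents give no expected mortality, no loss rate and no calculation behind the 200, so there is no planned figure to reproduce.

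**Rule logic.** The rule was applied to each pattern under two readings: (a) *Otherwise* limited to non-attenders who died; (b) *Otherwise* as a catch-all.

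| Day 90 visit | Death record | Reading (a) | Reading (b) |
|---|---|---|---|
| Completed | None | Alive | Alive |
| Completed | Day 100 | Alive | Alive |
| Missed | Day 60 or Day 104 | Dead | Dead |
| Missed | Day 110 | Alive | Alive |
| Missed | None | No status | Dead |

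Only the last pattern separates the readings. Under (a) the subject is either left in N, and so acts as a survivor, or is removed from N. Table 11 neither states nor rules out removal.

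**Inputs.**
- N = 200 (SAP 4: "Two hundred subjects will be enrolled at up to 15 centers in China").
- Mortality among subjects of known status: 20.0% (TREVO, 12/60, Protocol Table 1) or 33.0% (TREVO 2 Trevo arm, 29/88, Protocol Table 4), used as reference values.
- Lost subjects L: not given. Assumed at 1%, 5% and 10%, and unrelated to death.

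**Formulas.** Known deaths D = rate × (200 − L), rounded. Lost as dead: (D + L)/200. Lost as survivors: D/200. Lost excluded: D/(200 − L). The gap between the extremes is L/200.

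| Rate | L | D | Lost as dead | Lost as survivors | Lost excluded | Gap (points) |
|---|---|---|---|---|---|---|
| 20% | 2 | 40 | 42/200 = 21.0% | 40/200 = 20.0% | 40/198 = 20.2% | 1.0 |
| 20% | 10 | 38 | 48/200 = 24.0% | 38/200 = 19.0% | 38/190 = 20.0% | 5.0 |
| 20% | 20 | 36 | 56/200 = 28.0% | 36/200 = 18.0% | 36/180 = 20.0% | 10.0 |
| 33% | 2 | 65 | 67/200 = 33.5% | 65/200 = 32.5% | 65/198 = 32.8% | 1.0 |
| 33% | 10 | 63 | 73/200 = 36.5% | 63/200 = 31.5% | 63/190 = 33.2% | 5.0 |
| 33% | 20 | 59 | 79/200 = 39.5% | 59/200 = 29.5% | 59/180 = 32.8% | 10.0 |

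At 20% mortality, coding the lost as survivors understates the known-status rate by 20.0 − 19.0 = 1.0 point at 5% loss and 20.0 − 18.0 = 2.0 points at 10%. At 33% and 10% loss the figure is 32.8 − 29.5 = 3.3 points.

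**Which loss rate is plausible.** The quoted mortality denominators are 60 of 60 in TREVO, and 88 of 88 and 89 of 90 in TREVO 2. If they count subjects of known status, unknown vital status was 0%, 0% and 1/90 = 1.1%. Day 90 mRS in TREVO 2 was available for 85 of 88 and 87 of 90, so 3.4% and 3.3% were missing.

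**Double status.** The number of subjects with a Day 30 mRS of 0-2 who die later cannot be estimated from the documents. This gap is shown by reading alone.

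**The case against.** The strongest objection concerns the wording. Sentences 2 to 4 of the rule run in sequence: missed the visit and died, compare dates; died after the window, alive; otherwise, dead. Read that way, *Otherwise* means died on or before Day 104 and does not reach people with no death record. This stands. A reader might infer that the SAP instructs counting living lost subjects as deaths, but the text does not establish that. The lost-as-dead column holds only under the less natural reading.

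A reader might also infer that Table 11 must contradict itself for a subject who had a Day 30 mRS of 1 and was then lost. That too needs the catch-all reading. The conflict for a known later death does not, because it arises from the missing order between death coding and LOCF.

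The loss rates of 5% and 10% are high against the mortality denominators quoted from the earlier studies. Protocol 8.6.2 accepts a telephone mRS at Day 90, and deaths are recorded at every follow-up contact, so few subjects may end with unknown status. This also stands, and it limits the size. It does not supply the missing status.

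Finally, the endpoint is secondary and descriptive, with no hypothesis test, and the primary endpoint is untouched. That bears on priority, not on whether the rule is complete.

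**Conclusion.** The gap is real, and neither document closes it. A Day 90 non-attender with no recorded death becomes a death under one reading. Under the more natural reading that subject has no status and, given SAP 3, counts as a survivor unless excluded.

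The spread between the extremes is lost/200: about 1 point at 1% loss, 5 at 5% and 10 at 10%. A distortion of 5 to 10 points is not shown by the documents, because it needs an assumed 5 to 10% loss and the catch-all reading. Under the natural reading with the lost kept as survivors, mortality is understated by about 1 to 2 points at 20% mortality and 5 to 10% loss. All of these figures assume that loss is unrelated to death.

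The missing link between a known death and the LOCF mRS is a separate, smaller defect that holds under either reading. Both should be corrected before analysis; neither affects the primary endpoint.

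**What to change.** In SAP 5.2.2, keep the sentence that a completed Day 90 visit means alive, and say that it covers clinic or telephone contact within the window. Replace the *Otherwise* sentence with:

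*A subject is a death only if a date of death on or before the endpoint cut-off is recorded. A subject known to be alive after the cut-off is alive. A subject with no completed Day 90 visit, no recorded death and no later contact has unknown vital status.*

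State which rule takes precedence if a death is recorded after a completed visit but before the cut-off; at present the visit does.

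Unknown status should not be defined simply as no contact at or after the cut-off. The visit window runs from Day 76 to Day 104, so with a Day 104 cut-off that wording would turn completers seen on Days 76 to 103 into unknowns.

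In Table 11, report mortality among subjects with known status. A Kaplan-Meier estimate that censors unknowns at the last date known alive would also serve. Add the number of unknowns and the two bounds: all unknown alive and all unknown dead. Define N.

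For mRS, state that a subject classed as a death by the cut-off is scored 6 at Day 90 before LOCF is applied. Add a check that no subject is both mRS 0-2 and dead.

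The cost is a few sentences and a few lines of code, using dates already collected. The main estimate will assume uninformative loss, and the bounds make that assumption visible.

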**Table 3. Primary Endpoint Results per the TREVO 2 (ITT population)**

Endpoint	Trevo (N=88)	Merci (N=90)	Difference [95% CI] a	p-value
Primary Effectiveness Endpoint:				
Post-Device Revascularization Success (TICI 2a+)*	86.4% (76/88)	60.0% (54/90)	26.4% [13.2%, 39.0%]	< 0.0001 b < 0.0001 c
Primary Safety Endpoint:				
Composite Events ***	14.8% (13/88)	23.3% (21/90)	-8.6% [-20.7%, 3.2%]	0.1826 d
Vessel Perforation	1.1% (1/88)	10.0% (9/90)	-8.9% [-17.0%, -2.2%]	
Intramural Arterial Dissection	0.0% (0/88)	1.1% (1/90)	-1.1% [-6.1%, 3.1%]	
Symptomatic ICH	6.8% (6/88)	8.9% (8/90)	-2.1% [-10.7%, 6.4%]	
Embolization to Previously Uninvolved Territory	6.8% (6/88)	4.4% (4/90)	2.4% [-5.0%, 10.3%]	
Access Site Complication Requiring Surgical Repair or Blood Transfusion	2.3% (2/88)	1.1% (1/90)	1.2% [-4.0%, 6.9%]	
Mortality within 24 hours	2.3% (2/88)**	0.0% (0/90)	2.3% [-1.9%, 7.9%]	
In vivo Device Failure	0.0% (0/88)	0.0% (0/90)	0.0% [-4.1%, 4.2%]	

**STRYKER CONFIDENTIAL - THIS DOCUMENT CONTAINS CONFIDENTIAL AND PROPRIETARY INFORMATION THAT IS THE PROPERTY OF STRYKER CORPORATION. NEITHER THIS DOCUMENT NOR THE INFORMATION HEREIN MAY BE REPRODUCED, USED, OR DISCLOSED TO ANY THIRD PARTY WITHOUT THE PRIOR WRITTEN CONSENT OF STRYKER CORPORATION.**

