**Table 4. Secondary Endpoints in TREVO 2 (ITT population) **

Endpoint	Trevo (N=88)	Merci (N=90)	Difference [95% CI] a	p-value
Time to Revascularization (mins) b Mean ± SD (N) Median (min, max)	47.8±44.2 (79) 34.0 (6.0, 209.0)	47.3±38.8 (81)40.0 (4.0, 207.0)	0.5 [11.4%] c	< 0.0001 d 0.5326 e
90-Day Good Outcome (Modified Rankin Score 0-2)	40.0% (34/85)	21.8% (19/87)	18.2% [ 4.2%, 31.7%]	0.0130 f
90-Day Mortality	33.0% (29/88)	23.6% (21/89)	9.4% [ -4.2%, 22.7%]	0.1845 f
Asymptomatic ICH at 24 hours	40.9% (36/88)	53.3% (48/90)	-12.4% [-27.1%, 2.5%]	0.1017 f
Neurological Deterioration at 24 hours g	15.9% (14/88)	22.2% (20/90)	-6.3% [-18.4%, 5.5%]	0.3418 f

a: By normal approximation; b: Time to Revascularization was defined as the time from the start of the embolectomy procedure to achieving durable TICI 2a or better or to the end of the procedure if TICI 2a was not achieved. Subjects who had a baseline TICI score of 2a or did not have a study device used are excluded from this analysis (7 cases in Trevo arm, 8 cases in Merci arm); c: Per hypothesis testing setup, one-sided 95% upper confidence interval is used; d: One-sided Student's t-test of non-inferiority test with non-inferiority margin of 0.5 hours; e: One-sided Student's t-test of superiority test; f: Fisher's exact test; g: Defined as a four or more point increase in the NIHSS at 24 hours as compared to the baseline.

Overall the results of the TREVO and TREVO 2 trials demonstrate revascularization efficacy and safety of the Trevo Retriever.

**STRYKER CONFIDENTIAL - THIS DOCUMENT CONTAINS CONFIDENTIAL AND PROPRIETARY INFORMATION THAT IS THE PROPERTY OF STRYKER CORPORATION. NEITHER THIS DOCUMENT NOR THE INFORMATION HEREIN MAY BE REPRODUCED, USED, OR DISCLOSED TO ANY THIRD PARTY WITHOUT THE PRIOR WRITTEN CONSENT OF STRYKER CORPORATION.**

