### 5.2 Secondary Endpoints

- a. Day 90 mRS (good clinical outcomes defined as mRS of 0-2)
- b. Day 90 mortality
- c. Neurological deterioration at 24 hours, defined as a four or more point increase in the NIHSS score from the baseline score
- d. Rates of device and procedure related serious AEs

**STRYKER CONFIDENTIAL - THIS DOCUMENT CONTAINS CONFIDENTIAL AND PROPRIETARY INFORMATION THAT IS THE PROPERTY OF STRYKER CORPORATION. NEITHER THIS DOCUMENT NOR THE INFORMATION HEREIN MAY BE REPRODUCED, USED, OR DISCLOSED TO ANY THIRD PARTY WITHOUT THE PRIOR WRITTEN CONSENT OF STRYKER CORPORATION.**

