### 8.4 24 hours (-6/+24) post procedure

The following data will be collected at 24 hours (-6/+24) post procedure:

- NIHSS (see **appendix G**)
- SAEs related to the device or procedure.

**STRYKER CONFIDENTIAL** - THIS DOCUMENT CONTAINS CONFIDENTIAL AND PROPRIETARY INFORMATION THAT IS THE PROPERTY OF STRYKER CORPORATION. NEITHER THIS DOCUMENT NOR THE INFORMATION HEREIN MAY BE REPRODUCED, USED, OR DISCLOSED TO ANY THIRD PARTY WITHOUT THE PRIOR WRITTEN CONSENT OF STRYKER CORPORATION.

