## Trevo® Retriever Registry (China)

- For all subjects who expire prior to the 24 hours (-6/+24) assessment, available information regarding the primary cause of death and date/time of death will be recorded, as well as, whether the subject was made “do not resuscitate” (DNR) or “comfort care only” prior to expiration.

Any death or SAE must be reported to Stryker Neurovascular within 24 hours of becoming aware of the event(s).

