## Trevo® Retriever Registry (China)

### Appendix B. Definitions

Adverse Event (AE):	Any unintended disease or injury or untoward clinical sign in a research subject. NOTE - This definition does not imply that there is a relationship between the adverse event and the device under investigation.
Device Malfunction/Nonconformity:	The failure of a device to meet its performance specifications or otherwise perform as intended. Performance specifications include all claims made in the labeling for the device. The intended performance of a device refers to the intended use for which the device is labeled or marketed.
Embolization to New Territory:	Embolization into a previously uninvolved area of the brain, e.g. ACA embolization during MCA-M1 thrombectomy procedure.
Good Clinical Outcome:	A measure of neurologic functional outcome with a score of 0–2 on the modified Rankin Scale (mRS), usually assessed 90 days after treatment.
Irreversible Neurological Deterioration:	Neurological deterioration that is more than transitory, and is not related only to sedation. The neurological deterioration persists even after removal of sedation.
Modified Rankin Scale (mRS):	Scale for measuring the degree of disability or dependence in the daily activities of people who have suffered a stroke or other causes of neurological disability.
NIHSS Scale:	An assessment to objectively quantify the impairment caused by a stroke. It is composed of 11 items, each of which scores a specific ability between a 0 and 4. For each item, a score of 0 typically indicates normal function in that specific ability, while a higher score is indicative of some level of impairment. The individual scores from each item are summed in order to calculate a subject's total NIHSS score. The maximum possible score is 42, with the minimum score being a 0.
Pre-stroke disability:	Obtained at baseline, is representative of the subject's status before the index stroke, assessed by mRS on medical history obtained from subject, medical chart, or family members.
Protocol Deviation:	This protocol does not require specific interventions, therefore the term deviation will only be used to describe the following situation: Failure to obtain informed consent per Good Clinical Practices (GCP).

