#### 5.4.4. NIHSS

NIHSS will be summarized by mean  $\pm$  SD, median, minimum and maximum and by visits.

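### 24-hour neurological deterioration is defined by NIHSS change alone, so a subject who dies before that assessment cannot count as deteriorated and the rate is understated

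*SAP*

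**What the plan says.** SAP 5.2.2 item 3 describes the endpoint as "defined as four or more points increase in the NIHSS score from the baseline to 24 hours post procedure". Protocol 5.2 item c reads "Neurological deterioration at 24 hours, defined as a four or more point increase in the NIHSS score from the baseline score", and the protocol synopsis gives the same rule. None of the three mentions death.

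Protocol Appendix B describes the NIHSS: "The maximum possible score is 42, with the minimum score being a 0". No value stands for death, whereas the mRS in Appendix F has grade 6 for it.

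Protocol 8.4 sets the timing: "The following data will be collected at 24 hours (-6/+24) post procedure", that is, 18 to 48 hours. The same section provides for earlier deaths: "For all subjects who expire prior to the 24 hours (-6/+24) assessment, available information regarding the primary cause of death" is recorded, with the date and time of death and whether care had been limited beforehand. No NIHSS value is assigned.

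The SAP has one rule for classifying deaths, for Day 90 mortality (5.2.2 item 2), and one imputation rule, last observation carried forward for Day 90 mRS (Table 11 footnote). Neither covers the 24-hour NIHSS. SAP section 3 keeps every enrolled subject in all analyses. Table 11 shows n/N for this endpoint without defining N.

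For the scale itself, SAP 5.4.4 says "NIHSS will be summarized by mean" with SD, median and range, by visit.

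**The concern.** The endpoint is a difference between two scores, and a subject who dies before the second score has no difference. Two readings remain, and the documents do not choose between them. If a missing NIHSS means exclusion, the subject leaves the denominator, which sits badly with SAP section 3. If section 3 governs, the subject stays in the denominator and is reported as not deteriorated. Carrying the last score forward would not help: it would repeat the baseline value and give a change of zero.

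Either way, the worst early courses cannot be events in an endpoint meant to count early worsening, so the bias is always downward. This matters in a registry that sets out to follow safety and pick up uncommon complications. Because N is undefined, the choice would also be made after the data are known.

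The same limit applies to SAP Table 8: NIHSS means at 24 hours and at discharge can include only subjects alive to be examined, and the number who died is not shown beside them.

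**Working it through.** The documents state no expected rate, event count or precision for this endpoint, so there is no design figure to reproduce. The inputs below come from the Trevo arm of TREVO 2 and are used as assumptions.

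**Inputs**
- "Mortality within 24 hours" (Protocol Table 3): 2/88 = 2.3%, as printed. Clopper-Pearson 95% CI 0.3% to 8.0%.
- "Neurological Deterioration at 24 hours" (Protocol Table 4): 14/88 = 15.9%, as printed.
- Planned enrolment (SAP section 4): N = 200.

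**Step 1: how many subjects.** Expected early deaths: 200 × 2/88 = 4.5. Chance of at least one: 1 − (86/88)^200 = 99%. At the interval limits the expected number is about 0.6 (200 × 0.0028) or 16 (200 × 0.080). At the lower limit the chance of any such death is 1 − (1 − 0.0028)^200, about 43%.

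**Step 2: effect on the rate.** Let d be the deaths before the assessment, e the deteriorated among the other N − d subjects (all assumed to have a 24-hour NIHSS), and r = e/(N − d).
- Deaths excluded: rate e/(N − d); shortfall (e + d)/N − e/(N − d) = (d/N)(1 − r).
- Deaths kept as non-events: rate e/N; shortfall d/N.
- Deaths counted as deteriorated: rate (e + d)/N.

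Holding deterioration among the others at 15.9%, with e rounded to whole subjects:

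| Early deaths d | e | Excluded | Non-event | Counted | Shortfall (points) |
|---|---|---|---|---|---|
| 2 (1%) | 32 | 32/198 = 16.2% | 32/200 = 16.0% | 34/200 = 17.0% | 0.8 to 1.0 |
| 5 (2.3%, rounded up) | 31 | 31/195 = 15.9% | 31/200 = 15.5% | 36/200 = 18.0% | 2.1 to 2.5 |
| 10 (5%) | 30 | 30/190 = 15.8% | 30/200 = 15.0% | 40/200 = 20.0% | 4.2 to 5.0 |

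In the middle row the missed deaths are 5/36 = 14% of all events. The 95% CIs are 11.1% to 21.8% (excluded), 10.8% to 21.3% (non-event) and 12.9% to 24.0% (counted).

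**Step 3: cross-check on TREVO 2's own counts.** Table 4 does not say whether the 2 early deaths are among the 14.
- If both are: 14/88 = 15.9% with deaths counted, against 12/86 = 14.0% or 12/88 = 13.6% without.
- If neither is: 16/88 = 18.2% with deaths counted, against 14/86 = 16.3% or 14/88 = 15.9% without.

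The shortfall is again about 2 points, roughly 10% to 14% of the rate.

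**The case against.** **The deaths are recorded elsewhere.** A reader might infer that early deaths vanish from the registry's safety picture. The documents do not support that. Day 90 mortality is its own secondary endpoint with its own rule, Protocol section 14 requires reporting of fatal SAEs through Day 90, and SAP Table 12 tabulates SAEs by relatedness. This stands and limits the reach of the point. It does not correct the deterioration rate.

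**Comparison with TREVO 2.** A reader might infer that the registry's rule breaks comparability with TREVO 2's 14/88, because that denominator kept all 88 subjects despite 2 early deaths. The documents do not support this either. Footnote g of Protocol Table 4 gives the same NIHSS-only definition, and a full denominator does not show that the deaths were events. If they were non-events there, counting deaths here would make the two figures less alike. This is the reason to report both rates.

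**Adding death changes the endpoint.** Death from any cause includes non-neurological deaths. That is a fair cost, but cause of death is collected and can be listed.

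**The size is soft.** It rests on 2 events. The window also cuts both ways: a subject examined at 18 hours who dies at 20 is assessable, while deaths up to 48 hours can be affected. A shift of about 2 points is small beside an interval of roughly 11% to 22%, and no hypothesis or threshold depends on this endpoint. All of this stands, but the direction of the bias is unaffected.

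**Attrition is partly visible.** Table 8 prints N with each mean, Table 1 gives reasons for uncompleted visits, and the templates may change. Deaths are still not shown beside the means.

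**Conclusion.** The point holds. Under the written definition, a subject who dies before the 24-hour assessment cannot be counted as deteriorated, and no other rule repairs this. It is more than a missing detail, because both available readings understate the rate.

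The likely size is about 2 percentage points, with about 4 to 5 of 200 subjects affected, if early mortality resembles the TREVO 2 Trevo arm. For early death rates of 1% to 5% the range is about 1 to 5 points. These figures assume 15.9% deterioration among the remaining subjects and a 24-hour NIHSS for each of them. The documents give no expected rates for this registry. A subject examined within the window who dies afterwards is not affected.

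The conclusion concerns this secondary endpoint and the interpretation of Table 8. It does not extend to the registry's capture of deaths or to a demonstrated mismatch with TREVO 2.

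**What to change.** - In SAP 5.2.2 item 3 and the matching row of Table 11, define the event as *an NIHSS rise of at least 4 points from baseline at 24 (-6/+24) hours, or death before that assessment*. Set N as enrolled subjects with a 24-hour NIHSS or an earlier death.
- Make the same clarification in the protocol synopsis and Protocol 5.2 item c. Changing the SAP alone would leave the two documents in conflict.
- Report the NIHSS-only rate as a sensitivity analysis, with its denominator stated, since that is the definition TREVO 2 gives.
- Report the number of subjects without a 24-hour NIHSS, by reason, and list the cause of each early death counted as an event.
- In Table 8, show the number of deaths before each visit and label the summaries as covering survivors assessed.

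No new data are needed, because the date, time and cause of death are already collected. The costs are a small protocol wording change as well as the SAP edit, a slightly less favourable reported rate, and the inclusion of some deaths that may not be neurological.
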